7.6.2 Microbiological Response

An overall per-subject microbiological response will be determined at the Posttreatment Visit (7 [\pm 4] days) following EOT and EOS (if available) based on available information provided by the site's SOC for this population.

7.6.2.1 Microbiological Outcomes

An overall per-subject microbiological outcome for the specimens collected and obtained at any time after initiation of study treatment will be determined based on the individual microbiological outcomes for each baseline Gram-negative pathogen. The microbiological outcomes determined by investigator will also be entered in the eCRF. Emergent (ie, nonbaseline) pathogens are considered separately, and do not affect the per-subject microbiological outcome.

7.6.2.1.1 HAP/VAP/cIAI and BSI/Sepsis

- **Eradication:** Absence of the baseline Gram-negative pathogen from an appropriate clinical specimen. If it is not possible to obtain an appropriate clinical culture and the subject has a successful clinical outcome, the response will be presumed to be eradication.
- **Persistence:** Continued presence of the baseline Gram-negative pathogen from an appropriate clinical specimen.
- **Indeterminate:** No culture obtained from an appropriate clinical specimen or additional antibiotic therapy for the treatment of the current infection including missed sampling.

7.6.2.1.2 cUTI

- **Eradication:** A urine culture shows the baseline Gram-negative uropathogen found at entry at $\geq 10^5$ colony forming units (CFU)/mL are reduced to $< 10^3$ CFU/mL.
- **Persistence:** A urine culture shows that the baseline Gram-negative uropathogen found at entry at $\geq 10^5$ CFU/mL grows $\geq 10^3$ CFU/mL.

- **Indeterminate:** No urine culture obtained or additional antibiotic therapy for the treatment of the current infection including missed sampling.

7.7 Appropriateness of Measurements

The proposed safety assessment (physical examinations, vital sign measurements, and clinical laboratory tests) and timing of assessments are considered appropriate to adequately monitor and assess the safety of cefiderocol in paediatric subjects 3 months to < 18 years of age. The assessments of safety are typical for research studies in adults and therefore are also considered to be appropriate to provide a comprehensive assessment of safety in the paediatric population. Because cefiderocol is not associated with a risk for QTcF prolongation based on a negative thorough QT/QTc study (Study 1603R2116), ECGs will not be performed in the current study.

The proposed blood sampling scheme for determination of plasma cefiderocol concentrations is considered sufficiently accurate to estimate PK parameters in the paediatric population using a population PK model.

Efficacy parameters are exploratory study objectives, considering that the primary objectives of the current study are safety and PK (to confirm dosing recommendations) in paediatric subjects 3 months to < 18 years of age. Additionally, because the study is open label and because cefiderocol will be administered concurrently with SOC antibiotics, efficacy assessments will intentionally be not rigorous, but rather obtained to provide supplemental information regarding the use of cefiderocol in the paediatric population clinically.

7.8 Acceptable Time Windows

Measurements for safety, PK, and efficacy endpoints will be performed according to the schedule of assessments in [Appendix 1](#). The time windows displayed in [Table 7-7](#) are the acceptable time windows for information collection; time windows for analyses will be stated in the statistical analysis plan (SAP). The actual sampling date and time will be recorded in the eCRF.

Table 7-7 Acceptable Time Windows

Study Activity	Time Points		Acceptable Time Window
Screening	Can be Treatment Day 1		Within 4 days prior to Treatment Day 1
Enrollment	Treatment Day 1		---
Drug infusion	See Appendix 1		± 15 minutes
Dosing interval	See Appendix 1		± 15 minutes
Pharmacokinetic blood sampling	Cohorts 1 and 2	1 hour after start of infusion	± 15 minutes
		3 hours after start of infusion	Within 15 minutes prior to the end of infusion using a separate line or immediately after the end of infusion using the same line and with proper flushing
		3.5 hours after start of infusion	± 15 minutes
		5 and 8 hours after start of infusion	± 30 minutes
	Cohorts 3 and 4	3 hours after start of infusion	Within 15 minutes prior to the end of infusion using a separate line or immediately after the end of infusion using the same line and with proper flushing
		5 and 8 hours after start of infusion	± 30 minutes
EOT	Within 24 hours after last day of study treatment		As soon as possible after last dose (same calendar day)
Posttreatment	7 days after EOT		± 4 days
EOS	28 days after last dose of study treatment		+ 7 days

EOS = End of Study; EOT = End of Treatment

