1.2 Clinical Pharmacology Studies

To date, a total of 212 healthy adult subjects or subjects with impaired renal function who participated in 6 completed clinical pharmacology studies (a single-and multiple-ascending dose study [Study 1203R2111], an intrapulmonary pharmacokinetic (PK) study [Study 1214R2112], a renal impairment study [Study 1222R2113], a mass balance study [Study 1516R2114], a thorough QT/QTc study [Study 1603R2116], and a 3-part drug interaction study [Study 1521R2115]) have received single doses of cefiderocol ranging

from 100 to 4000 mg (4 g) or multiple doses of up to 2000 mg (2 g) for up to 10 days, infused intravenously (IV) over 1 or 3 hours.

In general, cefiderocol was safe and well tolerated in clinical pharmacology studies. There were no treatment-related or dose-dependent trends in vital sign measurements, electrocardiogram (ECG) parameters, or clinical laboratory test results. There were no deaths or serious adverse events (SAEs) reported in any study. Adverse events (AEs) occurred relatively infrequently and were mostly mild in severity, and almost all resolved spontaneously without intervention. There were no dose-dependent trends in the frequency or type of AEs reported.

Cefiderocol is associated with linear PK, has a relatively short apparent terminal half-life ($t_{1/2,z}$), and is primarily excreted unchanged in the urine. A summary of the PK profile for cefiderocol is provided; additional details are provided in the current version of the IB.

- After administration of a single 2000-mg dose of cefiderocol infused over 3 hours, the geometric mean and coefficient of variation (CV% of geometric mean) of cefiderocol maximum plasma concentration (C_{max}) and area under the concentration-time curve (AUC) extrapolated to infinity (AUC_{0-inf}) were 89.7 $\mu\text{g/mL}$ (20.5%) and 386.1 $\mu\text{g}\cdot\text{hr/mL}$ (17.2%), respectively. The C_{max} and AUC increased in a dose-proportional manner within the dose range from 100 to 2000 mg and 2000 to 4000 mg.
- After administration of 1000- and 2000-mg doses of cefiderocol every 8 hours (q8h), no accumulation for the C_{max} (ratio of C_{max} [Day 10/Day 1]: 1.07 to 1.08-fold) or AUC over the dosing interval τ ($AUC_{0-\tau}$) (ratio of $AUC_{0-\tau}$ [Day 10/Day 1]: 1.05 to 1.16-fold) was observed. Steady state was attained within 1 day after the start of multiple dose administration.

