- After administration of a single 1000-mg dose of [^{14}C]-cefiderocol infused over 1 hour, the majority of total radioactivity in plasma was accounted for intact drug. Additionally, 98.6% and 2.8% of the administered dose was excreted in urine and feces, respectively, with an overall recovery of total radioactivity (urine and feces combined) of 101.4% of the administered dose. More than 90% of the dose was excreted as unchanged cefiderocol in urine.
- After administration of a single 2000-mg dose of cefiderocol infused over 3 hours, the apparent terminal elimination half-life ($t_{1/2,z}$) of cefiderocol was 2.4 hours. A similar $t_{1/2,z}$ of 2.74 hours was estimated after administration of a single 2000-mg dose of cefiderocol infused over 1 hour (Study 1203R2111).
- Cefiderocol did not increase the C_{max} or AUC of furosemide (for OAT1 and OAT3) and metformin (for OCT1, OCT2, and MATE2-K). Cefiderocol increased the C_{max} and AUC of rosuvastatin (for OATP1B3) by 1.28-fold (90% CI, 1.12 to 1.46) and 1.21-fold (1.08 to 1.35), respectively (Study 1521R2115). These results suggest no clinically significant drug-drug interaction potential via these transporters.

- There was no clinically meaningful effect of age, sex, race, or body weight on the PK of cefiderocol based on a population PK analysis. No dose adjustment of cefiderocol based on demographic characteristics is considered to be necessary.
- A dedicated study to assess the potential effect of hepatic impairment on the PK of cefiderocol was not conducted. However, the need for a dose adjustment in subjects with hepatic impairment is not expected considering the primary route of elimination for cefiderocol is renal excretion.
- After administration of a single 1000-mg dose of cefiderocol infused over 1 hour, the geometric least squares mean ratios (GMRs) [renal impairment/normal renal function] and their 90% CIs for the AUC_{0-inf} of cefiderocol for subjects with mild, moderate, severe and end-stage renal disease (ESRD) requiring hemodialysis (HD) were 1.0 (0.8 to 1.3), 1.5 (1.2 to 1.9), 2.5 (2.0 to 3.3), and 4.1 (3.3 to 5.2), respectively. Dose adjustment of cefiderocol in subjects with renal impairment or augmented renal clearance is recommended.
- The 3- to 4-hour HD removed approximately 60% of cefiderocol dose. A supplemental dose immediately following HD is therefore recommended.

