In the single-dose phase, cefiderocol will be administered (in addition to SOC) at any time during the SOC treatment regimen. In the multiple-dose phase, cefiderocol will be administered on Day 1 (in addition to SOC), within 72 hours of the start of potentially effective treatment with SOC antibiotics for infection. Subjects will subsequently receive cefiderocol every 8 hours (q8h) for an expected 5 to 14 days; the total duration of cefiderocol administration will be determined by the investigator based on clinical assessment of each subject’s infection status. Each dose of cefiderocol will be administered IV over 3 hours. The infusion may be shortened if this is in the best interest of the subject and if approved by the sponsor via the Request for Shortened Infusion Duration Form. The single-dose phase will include only those subjects with normal renal function or mild renal impairment. The dose of cefiderocol for the single-dose phase will be determined based on body weight only; the maximum dose to be administered is not to exceed 2000 mg. The dose for the multiple-dose phase will be determined based on both body weight and renal function; the maximum dose to be administered is not to exceed 2000 mg. The SOC administered will be selected by the investigator based on the

suspected or confirmed pathogen(s) for the infection in accordance with local standards and can be modified at any time during the subject's participation in the study at the investigator's discretion. In the multiple-dose phase, if the subject's infection is confirmed to be Gram negative only before starting treatment, monotherapy with cefiderocol may be allowed.

End-of-treatment (EOT) assessments will occur within 24 hours after administration of cefiderocol (single-dose phase) or within 24 hours after administration of the last dose of study treatment (multiple-dose phase), or at early termination. A further clinical assessment will occur at a Posttreatment visit 7 (\pm 4) days after EOT (multiple-dose phase), which is analogous to a TOC and EOS time point, if microbiological samples are available. The EOS visit will occur 28 (+ 7) days after administration of cefiderocol in the single-dose phase or 28 (+ 7) days after administration of the last dose of study treatment in the multiple-dose phase; this visit may be performed on-site or via phone call. The study schematic including a schedule of assessments is provided in [Figure 3-1](#) and [Table 3-2](#).

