Multiple-dose Phase (Cohorts 2, 3, and 4): In the multiple-dose phase, subjects will be administered doses of cefiderocol infused IV over 3 hours, q8h, beginning on Day 1 and continuing for an expected 5 to 14 days (in addition to SOC), within 72 hours of the start of potentially effective treatment with SOC antibiotics for infection. The total duration of treatment with cefiderocol will be determined by the investigator based on clinical assessment of each subject's infection status. The dose of cefiderocol administered to each subject will be based on both body weight and renal function ([Table 5-2](#)). No more than 2000 mg of cefiderocol should be administered. After initiation of cefiderocol administration, cefiderocol doses may be adjusted based on changes in renal function as assessed by eGFR (using the Schwartz equation [[10](#)] if ≥ 3 months to < 1 year of age and modified Bedside Schwartz equation [[11](#)] if ≥ 1 to < 18 years of age) and according to the dosing recommendations for subjects with moderate or severe renal impairment ([Table 5-3](#)). See [Section 7.5.3.1.2](#) for eGFR calculations and ranges.

Shorter infusion times may be allowed in the multiple-dose phase if agreed on by the sponsor via the Request for Shortened Infusion Duration Form, and if in the best interest of the subject. Infusion volume adjustments by age will be provided in the pharmacy manual.

In special circumstances, treatment beyond 14 days may be allowed following review and approval of individual cases by the Shionogi medical monitor. To apply for this, a Treatment Extension Form should be completed and submitted to the Shionogi medical monitor on Day 12 or earlier (if over the weekend) to ensure continuity of treatment.

In the multiple-dose phase, if the subject's infection is confirmed to be Gram-negative only before starting treatment, monotherapy with cefiderocol may be allowed.

Table 5-1 Dosing Limits for Cefiderocol in Single-dose Phase: Subjects with Normal Renal Function or Mild Renal Impairment

Cohort	Single-dose Phase Dose		Infusion Time
	Body Weight		
	≥ 34 kg	< 34 kg	
1 (12 to < 18 years of age)	2000 mg	60 mg/kg*	3 hours
2 (6 to < 12 years of age)	2000 mg	60 mg/kg*	3 hours
3 (2 to < 6 years of age)	2000 mg	60 mg/kg*	3 hours
4 (3 months to < 2 years of age)	2000 mg	60 mg/kg*	3 hours

* **No more than 2000 mg of cefiderocol should be administered.**

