7.4 Pharmacokinetic Assessments

Pharmacokinetic studies in the paediatric population are generally conducted in patients with the disease to obtain data that better reflect clinical use of cefiderocol. The PK analyses in this study are mandatory and are being performed to determine PK parameters in different age groups to support cefiderocol dosing recommendations.

The total volume of blood withdrawn per subject in this study has been kept at a minimum by using micro tubes. The PK sampling schedule also allows for some flexibility in Cohorts 1 and 2, in terms of number of samples (3 to 5 samples, See [Table 7-2](#) for PK sampling times).

Several approaches will be used to minimize the amount of blood drawn and/or the number of venipunctures:

- Due to the use of a sensitive assay for cefiderocol, the volume of blood required per sample is 180 μ L, ie, 0.18 mL (0.36 mL in total for primary sample and back-up)
- To minimize discomfort of blood sampling, sites will be encouraged to use topical anesthesia to place IV catheters, to use indwelling catheters rather than repeated venipunctures for blood sampling, and to collect PK blood samples at the same time as routine, clinical blood samples are obtained, when possible
- The study uses PK and central laboratories experienced in handling small volumes of blood for PK analyses and for laboratory safety studies

At each PK sampling time point, up to 0.4 mL of blood (but no less than 180 μ L, ie, 0.18 mL) will be obtained, adding up to the maximum volumes shown in [Table 7-1](#):

Table 7-1 Total PK Blood Sample Volumes

Cohorts	Cohort 1	Cohort 2	Cohort 3	Cohort 4	Cohorts 1 and 2 Flexible Sampling	
Age	12 years to < 18 years	6 years to < 12 years	2 years to < 6 years	3 months to < 2 years	3-point design	4-point design
Number of samples	5 samples	5 samples	3 samples	3 samples	3 samples	4 samples
Total PK Blood volume	2.0 mL	2.0 mL	1.2 mL	1.2 mL	1.2 mL	1.6 mL

PK = pharmacokinetic

Cohorts 1 and 2: A total of 5 blood samples for determination of plasma cefiderocol concentrations will be collected from each subject as specified in [Table 7-2](#). In the multiple-dose phase, sampling will be done during one of the dosing intervals from the 6th to the 12th dose of cefiderocol. In the multiple-dose phase of the study in Cohort 2, if approved by the sponsor and is in the subject's best interests, it is acceptable adjust the sampling time points to a minimum of 3 or 4 samples (versus ideally 5 samples).

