6.2.6. Nominal time

Nominal time will be defined as the scheduled measurement time relative to time 0. Time 0 will be the time of dosing for the treatment period of interest.

This document is confidential.

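### In the multiple-dose phase the ±30-minute window for the 8-hour PK sample overlaps the next q8h infusion, so an in-window sample can inflate the 8-hour concentration summaries

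*Protocol*

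**What the plan says.** Protocol Table 7-7 (Section 7.8) has one row for the samples due "5 and 8 hours after start of infusion" in Cohorts 1 and 2 and another in Cohorts 3 and 4. Both give ±30 minutes, and neither distinguishes the phases. SAP Table 6-1 (Section 6.5) repeats them. The same two tables give the dosing interval ±15 minutes.

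For the multiple-dose phase, Protocol 5.2 states that "subjects will be administered doses of cefiderocol infused IV over 3 hours, q8h". Section 3.1 agrees: "Subjects will subsequently receive cefiderocol every 8 hours (q8h) for an expected 5 to 14 days" and "Each dose of cefiderocol will be administered IV over 3 hours". On which dose to sample, Protocol 7.4 says for Cohorts 1 and 2 that "sampling will be done during one of the dosing intervals from the 6th to the 12th dose of cefiderocol", with parallel wording for Cohorts 3 and 4. Cohorts 3 and 4 have three samples, at 3, 5 and 8 hours.

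In the SAP, "Nominal time will be defined as the scheduled measurement time relative to time 0" (Section 6.2.6). Section 9.3.3 summarises and plots mean concentrations at nominal times. On grounds of timing, Section 9.3.1 allows exclusion only of samples far outside their window. It separately lets the PK scientist drop values judged anomalous, with justification.

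**The concern.** In the single-dose phase a sample 30 minutes late is a slightly later point on a falling curve. In the multiple-dose phase it can be a point on the rising limb of the next infusion. The windows make no distinction, so such a sample is compliant and is reported as an 8-hour value.

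The visible text contains no explicit pre-dose instruction for this sample, although the multiple-dose schedule in Appendix 1 (footnote f) does place a vital-sign measurement before the next dose. The SAP's timing exclusion does not reach the sample, because it is inside its window.

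Multiple-dose PK is a primary objective, and plasma concentration is the only PK endpoint listed in SAP 4.4 and 9.2. With a minimum of 10 subjects per multiple-dose cohort, a few such values would be visible in the 8-hour row.

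**Working it through.** **Timing.** The next infusion may start 7.75 to 8.25 h after the previous start. A sample at 8.5 h is then 8.5 − 8.25 = 0.25 h (15 min) to 8.5 − 7.75 = 0.75 h (45 min) into it. That range applies only to a draw at 8.5 h. At 8.25 h it is 0 to 30 min, and a draw at exactly 8.0 h is caught only if the next infusion is early.

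**Inputs (Protocol 1.2, adults).** The first anchor is the bullet beginning "After administration of a single 2000-mg dose of cefiderocol infused over 3 hours, the geometric mean and coefficient of variation", which gives AUC0-inf 386.1 µg·h/mL and Cmax 89.7 µg/mL. The second is the terminal half-life, which "of cefiderocol was 2.4 hours". Adult figures are a proxy; Protocol 5.3 says paediatric doses were set for comparable AUC.

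**One-compartment model**
- CL = 2000/386.1 = 5.18 L/h
- k = ln 2/2.4 = 0.289 per h
- Infusion rate/CL = (2000/3)/5.18 = 128.7 µg/mL
- End of first infusion: 128.7 × (1 − e^(−3k)) = 74.6 µg/mL

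**Check against the protocol's own figures.** The single-dose 8-h value is 74.6 × e^(−5k) = 17.6. The area beyond 8 h is 17.6/0.289 = 60.9, so AUC0-8 = 386.1 − 60.9 = 325.2. The AUC accumulation ratio is 386.1/325.2 = 1.19, or 1.13 if the infusion lasts 1 h. The protocol reports 1.05 to 1.16 without giving the infusion length. The modelled Cmax of 74.6 is below the stated 89.7. The model is adequate for scale, not for precision.

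**Steady-state 8-h value:** 74.6/(1 − e^(−8k)) × e^(−5k) = 19.5 µg/mL.

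**Sample at 8.5 h, next infusion starting at s:** C = 19.5 × e^(−0.5k) + 128.7 × (1 − e^(−k(8.5 − s))). The first term is 16.9. Ratios use unrounded values.

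| Next infusion starts | Concentration at 8.5 h (µg/mL) | Ratio to 19.5 |
|---|---|---|
| 8.25 h | 16.9 + 9.0 = 25.9 | 1.32 |
| 8.00 h | 16.9 + 17.3 = 34.2 | 1.75 |
| 7.75 h | 16.9 + 25.1 = 42.0 | 2.15 |

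**Half-life sensitivity** (same AUC, next infusion on time, sample at 8.5 h): 3.5 times at 1.5 h, 2.15 at 2.0 h, 1.57 at 2.74 h, 1.21 at 4.8 h.

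**Model sensitivity.** A two-compartment model matched to both AUC 386.1 and Cmax 89.7 gives an 8-h value of 13.4 to 14.1 and an on-time ratio of 2.8 to 4.1. It needs a distribution rate that the documents do not give (assumed 0.8 to 5 per h), so I rest nothing on it beyond noting that the one-compartment ratios are not obviously too high.

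**Weight in a summary.** The documents give no frequency of late draws. If one subject in ten were sampled at 8.5 h and the rest were at 19.5, the arithmetic mean would rise by (34.2 − 19.5)/(10 × 19.5) = 7.5% with the next infusion on time. The corresponding rises are 3.3% if it is 15 min late and 11.5% if 15 min early. The geometric mean would rise less: 1.75^0.1 = 1.058, or 5.8%, in the on-time case.

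**With a pre-dose rule.** The largest timing errors left are e^(0.5k) = 1.155 (+16%, sample at 7.5 h) and e^(−0.25k) = 0.930 (−7%, sample at 8.25 h just before a late infusion).

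**The case against.** The best defence is that the protocol already confines sampling to one dosing interval, and a sample drawn after the next infusion starts is no longer in it. This stands in part. A reader might infer that nothing calls for a pre-dose draw, but the interval wording does imply one. The fault is that the window contradicts that wording. The laboratory manual, to which Protocol 7.4 defers, and the PK analysis plan are not among the documents and may contain an explicit rule. Even so, these two tables define compliance and should match it.

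A second defence is that little depends on the affected output, and this largely stands. Protocol 7.7 and 9.10 look to a population PK model for parameters. Actual sampling times (7.4) and every infusion start (5.9) are recorded, so a model using both can absorb a late sample. The decisions to open Cohort 4 and the multiple-dose phase use single-dose data (SAP 2.3). There is no inferential testing, and individual profiles are plotted at actual times (SAP 9.3.2).

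A reader might also infer that the reported half-life would be distorted. Half-life is an endpoint in Protocol Section 2, but neither document plans to derive it from the slope between the 5-hour and 8-hour samples, so that inference is not supported.

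Third, the ratios are edge-of-window values on adult data, and there is no overlap when the sampled dose is the last one. That is correct and limits the size claimed. The PK scientist's discretion over anomalous values is a partial safeguard, but it is not tied to the start of the next infusion.

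**Conclusion.** The inconsistency is real and its reach is narrow. Following both documents exactly, a site can draw a compliant 8-hour sample during the next infusion, and the SAP can report it as an 8-hour value. Under a one-compartment model with adult AUC 386.1 and half-life 2.4 h, a draw at 8.5 h reads about 1.3 to 2.15 times 19.5 µg/mL. With the next infusion on time the ratio is 1.75, moving to about 1.2 at a half-life of 4.8 h and 3.5 at 1.5 h. These figures assume a 3-hour infusion; for shortened infusions the sampling times move under the laboratory manual, and I make no estimate.

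The harm is confined to the multiple-dose 8-hour rows of Table 14.2.2 and the corresponding points of Figure 14.2.3. The documents do not support reading it as a threat to the single-dose results, to the cohort decisions, or to a population PK analysis that uses actual sampling and infusion times. The severity is moderate: worth correcting before database lock, but not a fault that undermines the study's main PK conclusions.

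**What to change.** In Protocol Table 7-7 and SAP Table 6-1, split the 8-hour entry by phase. Leave the single-dose phase at ±30 minutes. For the multiple-dose phase, state ±30 minutes and always before the next infusion starts, and align the laboratory manual. A strict limit of −30 to 0 minutes is not needed: it would reject a valid pre-dose sample at 8.1 h when the next infusion starts at 8.25 h.

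In SAP 9.3.1, add a rule that any 8-hour sample drawn after the recorded start of the next infusion is flagged and left out of the nominal-time summaries and mean plots. Keep it in the listings and in the actual-time population PK analysis.

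The cost is one table entry in each document, one SAP sentence and a manual note. The SAP rule uses data already collected, and no dose, sample count or blood volume changes. The downside is that a few late samples will drop out of the 8-hour summary.
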